4.2. Secondary Objective

Blood pressure and antihypertensive medication related

1. To compare the mean change in systolic and diastolic blood pressure between the 2 groups from baseline to 6 months and 2 years post randomization
2. To compare the proportion of patients having adequate control of hypertension at end of 1 year and 2 years

3. Among those with adequate control, to compare the de-escalation of dose or reduction in the number of antihypertensive medications from baseline to 6 months, 1 year and 2 years in both the groups
4. To study the frequency of introduction of new antihypertensive medications or dose escalation of existing antihypertensive medications in both the groups

Metabolic parameters and biomarkers based

5. To study the effect of Twin Precision treatment on change on metabolic parameters
6. To study the effect of Twin Precision treatment on change in cardiac and renal biomarkers

Quality of life and Safety related

7. To study the safety of Twin Precision treatment on antihypertensive drug withdrawal
8. To compare the change in quality of life and treatment satisfaction between the 2 groups

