No other risk factors	Low	Low	Moderate/high
1 or 2 risk factors	Low	Moderate	High
≥ 3 risk factors	Low/moderate	High	High
HMOD, CKD grade 3, diabete, CVD	High	High	High

Stepwise approach will be followed for adding antihypertensive medications as follows at each visit. (Table- 3)

Step-1 Dual low dose combination	A+C
Step-2 Dual full dose combination	A+C
Step-3 Triple combination	A+C+D
Step-4 (Resistant hypertension) Triple combination + spironolactone or other drug	A+C+D Add spironolactone

A - ACE inhibitor / ARB

C - Calcium channel blocker

D - Diuretics

Supportive references: A+C, Spironolactone, Alpha blocker, C+D

Alternatives include: Amiloride, Doxazosin, Eplerenone, Clonidine or beta-blocker

7.3.2 Group B (Intervention arm):

Will receive Twin Precision nutrition along with standard of care medications for hypertension

Details of Twin Precision Treatment (TPT)

Patients randomized to the intervention group will follow the medicine, exercise, sleep and nutritional syntax of the Twin Precision Treatment program.

Twin Health platform and sensors

The Twin Health platform uses a Whole Body Digital Twin, powered by artificial intelligence and Internet of Things technology, to precisely understand the metabolic impairment in the patient's body, which is unique to the patient. The platform collects data from body sensors and a mobile app to track and analyze the body's health signals in order to personalize patients' treatment.

The Digital Twin precisely understands metabolic dysfunction by monitoring and correlating up to 3000 health data points collected each day through sensors and by integrating with the historical and ongoing patient health data. This is done by providing blood screens and health sensors including a CGM patch, sensor watch, wireless BP meter, BHB meter and body composition scale. The platform then recommends the precision treatment needed to heal the metabolism. The precise nutrition activity and sleep recommendations are presented in the Twin mobile app, which also provides the daily health progress of the patient from day 1.

Patients enrolled in TPT according to the eligibility criteria will be analyzed retrospectively. TPT is an outpatient program. During TPT enrolment, complete information on medical history, family history related to chronic conditions, weight, height and current medication details will be captured.

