Dose reduction or withdrawal of antihypertensive drugs will be considered when the patient reaches the target blood pressure. The dose reduction is in accordance with the protocol described by Nelson et al. i.e half dose reduction at weekly intervals with weekly assessment until the lowest dose is reached followed by withdrawal. The period of withdrawal will range from 2 weeks to 4 weeks.

Target blood pressure for our study will be considered as 130/80 mm Hg for young individuals and 140/90 mm Hg for elderly (65 and above) -2020 International Society for Hypertension Global Hypertension Practice Guidelines

Table-4 Antihypertensive medicines escalation and de-escalation protocol

Tier number	Medicines	Initial condition on enrolment	Reduction condition	Increase conditions
Tier 0	No medicine	Initial no medicine & BP < 160/100 mm Hg		Move to Tier 1, if (5d-BP > 135/85) & (after staying in this tier for 5 days)
Tier 1	Monotherapy (A)	Monotherapy	Move to Tier 0, if ((1d-BP < 135/85 for 7 consecutive days) II (1d-BP < 90/60 for 3 consecutive days) II (Symptoms of Hypotension like Postural Giddiness)) && (EOD-)	Move to Tier 2, if (5d-BP > 135/85) && (after staying in this tier for 5 days)
Tier 2	Dual low dose combination (A+C)	Dual low dose combination	Move to Tier 1, if ((1d-BP < 135/85 for 7 consecutive days) II (1d-BP < 90/60 for 3 consecutive days) II (Symptoms of Hypotension like Postural Giddiness))	Move to Tier 3, if (5d-BP > 135/85) && (after staying in this tier for 5 days)

Tier 3	Dual full dose combination (A+C)	Dual full dose combination/ Triple combination/ Triple combination + spironolactone or Alpha blocker	Move to Tier 2, if ((1d-BP < 135/85 for 7 consecutive days) II (1d-BP < 90/60 for 3 consecutive days) II (Symptoms of Hypotension like Postural Giddiness))	Move to Tier 4, if (5d-BP > 135/85) && (after staying in this tier for 5 days)
Tier 4	Triple combination (A+C+B/ D/ Alpha blocker)	Triple combination/ Triple combination + spironolactone or Alpha blocker	Move to Tier 3, if ((1d-BP < 135/85 for 7 consecutive days) II (1d-BP < 90/60 for 3 consecutive days) II (Symptoms of Hypotension like Postural Giddiness))	Consider manual change of medication or withdraw

A= ACE inhibitor or ARB

C = Calcium channel blocker

B = Beta blocker

D = Diuretics

Note:

- EOD (End organ damage) + =
1. LVH present
 2. Albuminuria
 3. Evidence of Heart failure
 - A. Low ejection fraction
 - B. High pro-BNP
 - C. Clinical features
 4. Hypertensive retinopathy

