9.2 Secondary outcome

Blood pressure and antihypertensive medication related

1. **Change in blood pressure (Clinical and ambulatory blood pressure)** from baseline to 6 months and 2 year. Ambulatory and clinic blood pressure monitoring will be done as mentioned in the primary endpoint.
2. **Adequate control of blood pressure** as measured by ambulatory blood pressure monitoring at 1 year and 2 years

Criteria for adequate control of blood pressure is

- In <65 years < 130/80 mm Hg
- In 65 and above < 140/90 mm Hg

3. Number of antihypertensive medications at 6 months, 1 year and 2 years

Among those with adequate control, the number of antihypertensive medications will be calculated at baseline (after run in period) and subsequently every 3 months. Combination pills containing more than one group (of antihypertensive medications) will be considered based on the number of groups. Example: Lotrel which is a combination of Amlodipine and benazepril will be considered as 2 drugs. Further each drug will be categorized as high dose or low dose.

Table-5 for doses of commonly used antihypertensive medications

Drug name	Dose 1	Dose 2	Dose 3	Dose 4
Losartan	25 mg	50 mg		
Telmisartan	20 mg	40 mg	80 mg	
Olmesartan	5 mg	20 mg	40 mg	
Candesartan	16 mg	32 mg		
Captopril	12.5 mg	25 mg	50 mg	100 mg
Enalapril	5 mg	10 mg	20 mg	40 mg
Lisinopril	5 mg	10 mg	20 mg	40 mg
Ramipril	1.25 mg	2.5 mg	5 mg	
Hydrochlorothiazide	12.5 mg	25 mg	50 mg	100 mg

Chlorthalidone	25 mg	50 mg	100 mg	
Indapamide	1.25 mg	2.5 mg	5 mg	
Frusemide	20 mg	40 mg		
Prazosin	1 mg	2.5 mg	5 mg	
Terazosin	1 mg	2 mg	5 mg	
Doxazosin	1 mg	2 mg	4 mg	
Propranolol	10 mg	20 mg	40 mg	
Metoprolol	25 mg	50 mg	100 mg	
Atenolol	50 mg	100 mg		
Bisoprolol	5 mg	10 mg		
Amlodipine	5 mg	10 mg		
Cilnidipine	5 mg	10 mg	20 mg	
Nicardipine	20 mg	40 mg	80 mg	
Nifedipine	30 mg	60 mg	90 mg	
Felodipine	2.5 mg	5 mg	10 mg	

4. Frequency of introduction of new antihypertensive medications or dose increment of existing antihypertensive medications will be noted across both the groups and compared.

Metabolic parameters and biomarkers based

5. Change in metabolic parameters

- Will include anthropometric assessment (Height, Weight, BMI, waist circumference, Waist hip ratio, visceral fat), lipid profile including lipoprotein (a), apolipoprotein - A1, apolipoprotein - B, insulin resistance (measured by HOMA- IR) every 3 months till end of study

6. Change in cardiac and renal biomarkers

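### Secondary outcome 3 grades dose only as high or low, so for 18 of the 24 drugs in Table 5 some one-level dose reductions cannot register, although objective 3 compares dose de-escalation and item 4 counts any increase

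*Protocol*

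**What the plan says.** Secondary objective 3 (Protocol 4.2) is confined to patients whose blood pressure is adequately controlled. Its aim reads "to compare the de-escalation of dose or reduction in the number of antihypertensive medications from baseline to 6 months, 1 year and 2 years". Dose reduction is thus named beside the number of drugs.

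The matching outcome (Protocol 9.2, item 3) is headed by the number of medications. It explains how combination pills are counted and then adds one sentence on dose: "Further each drug will be categorized as high dose or low dose". Table 5 follows under the columns "Drug name Dose 1 Dose 2 Dose 3 Dose 4". No column is labelled high or low. Some drugs have two levels ("Amlodipine 5 mg 10 mg"), some three ("Telmisartan 20 mg 40 mg 80 mg") and some four.

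Item 4 of the same section counts new drugs and dose increments of existing drugs, with no high/low restriction. Section 7.3.2 describes tapering in the intervention arm as "half dose reduction at weekly intervals with weekly assessment until the lowest dose is reached"; after that the drug is stopped.

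**The concern.** The objective asks whether doses come down. The taper lowers them in steps, and Table 5 already has a scale with up to four levels. The outcome then reduces that scale to two categories. A patient whose dose falls within one category has had a dose reduction that the stated measure shows as no change. The same move upwards would count under item 4, so decreases and increases are not measured alike.

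At stake is a secondary outcome that bears on one of the benefits the protocol anticipates, a lower medication burden. For the drugs with three or four levels the cut is also left open, and the trial is open label. But settling the cut would not cure the problem, because every cut hides some steps.

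**Working it through.** The protocol states no figure on this point, so there is nothing to reproduce. The check is a count from Table 5.

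**Rule.** A drug with *k* listed levels has *k* − 1 one-level reductions. A single high/low cut lies between two adjacent levels and is crossed by exactly one of them. So *k* − 2 reductions stay hidden, whichever cut is chosen.

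| Levels per drug | Drugs | One-level steps | Visible | Hidden |
|---|---|---|---|---|
| 2 | 6 | 6 × 1 = 6 | 6 | 0 |
| 3 | 14 | 14 × 2 = 28 | 14 | 14 |
| 4 | 4 | 4 × 3 = 12 | 4 | 8 |
| Total | 24 | 46 | 24 | 22 |

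Hidden: 22/46 = 47.8%. Drugs with at least one hidden step: 14 + 4 = 18 of 24.

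**Example.** Enalapril is listed at 5, 10, 20 and 40 mg. With a cut between 10 and 20, a fall from 40 to 20 stays high and a fall from 10 to 5 stays low; only 20 to 10 registers. A rise from 20 to 40 would be an increment under item 4. Amlodipine, with two levels, loses nothing.

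**Sensitivity to what counts as a step.**

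- Adding each drug's final step to zero, which the drug count records: 46 + 24 = 70 steps, and 22/70 = 31.4% hidden.
- All downward pairs, including falls of more than one level: 6 × 1 + 14 × 3 + 4 × 6 = 72. Depending on the cuts, 22 to 26 are hidden (30.6% to 36.1%).
- Only one-level steps that are exact halvings: 42 of the 46. Depending on the cuts, 18 to 22 are hidden (42.9% to 52.4%).

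If any within-drug decrease counted, none of the 46 steps would be lost.

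**The case against.** **The two-level label fits the treatment scheme.** In Table 4, the moves from Tier 4 to 3, 2 to 1 and 1 to 0 each lower the number of drugs, and the move from Tier 3 to 2 goes from full-dose to low-dose dual therapy. Drug count plus a high/low label captures these moves largely. This stands and narrows the point. But the tiers apply to the intervention arm, the low and full labels describe combinations rather than single drugs, and section 7.3.2 also provides for repeated halving.

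**A completed taper ends in withdrawal, which is counted.** Withdrawal is planned over 2 to 4 weeks, while the comparisons are at 6 months, 1 year and 2 years. This also stands. The loss concerns patients whose dose has come down but who still take the drug at the assessment. The protocol gives no basis for their number.

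**The analysis plan could set the cut or analyse the levels.** It could set the cut, so the unstated cut alone would be no finding, and fear of a cut chosen after seeing the data rests on a document not shown. But no cut recovers the hidden steps, and analysing the levels would replace the measure that the protocol states. The protocol does not say outright that a reduction within one category fails to count; that follows from high/low being the only dose measure given for item 3.

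**Stronger readings that the protocol does not support.**

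- A reader might infer that nearly half of patients' dose reductions would be missed. The 22 of 46 gives every listed drug equal weight, and there are no usage data.
- A reader might infer that drugs without a row, such as the one in Table 3 step 4 ("Add spironolactone"), cannot be classed at all. Table 5 is titled as covering commonly used drugs, and benazepril, from the outcome's own combination example, is not in it. It is not a closed list, and several of the alternatives under Table 3 (doxazosin, beta-blockers) do have rows.
- A reader might infer a quantified loss of power. None was calculated.

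**Conclusion.** The point holds as a mismatch between objective and measure. Objective 3 compares dose de-escalation, but the stated dose measure cannot show every one-level reduction for 18 of the 24 listed drugs, and item 4 counts increases without that limit. The size is 22 of 46 listed one-level steps, or 22 of 70 with the step to zero included.

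This assumes that high/low is the only dose measure used for item 3, that one cut is applied per drug, and that each drug and step has equal weight. The share of patients affected could be small if most take two-level drugs or have finished their taper by the assessment.

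This is a minor improvement to a secondary outcome. It does not touch the primary endpoint or the sample size.

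**What to change.** Replace the high/low sentence in 9.2, item 3, with:

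> For each drug, any decrease in recorded daily dose from baseline (including to zero) counts as de-escalation, on the same basis as dose increments in item 4; the proportion of patients with any de-escalation is compared between arms, with drug switches reported separately.

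Do not replace the label with a sum of Table 5 levels across drugs. The levels are not equivalent: the top listed level is 2 for amlodipine and 4 for enalapril, so a switch between the two at top level would halve the score and look like de-escalation.

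The cost is one sentence. No new data should be needed, since both the high/low label and item 4 already require doses to be known. The small downside is that drug switches need their own category.

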
Details of intervention (Twin Precision treatment)
 
The platform collects data from body sensors and a mobile app to track and analyze the body's health signals to personalize patients' treatment.
 
Individualized medicine, exercise, sleep and nutritional syntax of the Twin Precision Treatment program guided by artificial intelligence will be
	
Details of standard care (as per ISH 2020 guidelines)
 
Lifestyle modifications will focus on
 
 ● Weight loss for optimal BMI, ● Physical activity of 150 min/week ● Salt reduction ● Avoid smoking, alcohol 
Pharmacological therapy:
 
A= ACE inhibitor or ARB
 
B = Beta blocker

administered.	
C = Calcium channel blocker
 
D = Diuretics

Study population:
 
 ● Patients with hypertension ● Monotherapy or more than one drug as well not on medications ● Well-controlled or controlled 	
Key exclusion criteria
 
 ● Uncontrolled hypertension (> 180/110 mm of Hg) ● H/o hypertensive emergency requiring admission / Resistant Hypertension ● Diabetes mellitus ● Heart failure with EF < 40%

Primary outcome
 
Change in blood pressure* 1-year post-randomisation
 
* Both ABPM 24 hour and at clinic BP
	
Secondary outcomes
 
 ● Change in blood pressure* 6 months and two years post-randomisation ● Requirement of antihypertensive medications ● Change in metabolic parameters ● Inflammatory markers ● Hypertension mediated organ damage (Brain, cardiac, kidney and eye) assessment ● Major adverse Cardiac outcomes

Protocol signature page

Study title: Efficacy and safety of Twin Precision treatment in patients with hypertension- a multicentric, open-label, randomised controlled trial

I have read this protocol and agree that it contains all necessary details for carrying out the study as described. I will conduct the study as outlined therein, including all statements regarding confidentiality. I will make a reasonable effort to complete the study within the time designated. I will provide copies of this protocol and all pertinent information to the study personnel under my supervision. I will discuss this material with them and ensure they are fully informed regarding the device and the conduct of the study.

I will conduct the study in accordance with the protocol, the Declaration of Helsinki and applicable local requirements.

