Moderation of alcohol consumption and smoking cessation	
Counselling will be provided on the importance of cessation of smoking and alcohol consumption. Habitual drinkers will be advised on the moderation of amount and to avoid binge drinking. The recommended daily limit for alcohol consumption is 2 standard drinks for men and 1.5 for women (10 g alcohol/standard drink).

Management of blood pressure in standard care arm

Medication will be started or up titrated if blood pressure is > 140/90 mm Hg and treated to reach target blood pressure

Target blood pressure control will be(10)

Office

- In <65 years < 130/80 mm Hg
- In 65 and above < 140/90 mm Hg

ABPM

- 24 hr average \leq 130 and/or \leq 80
- Day time average \leq 135 and/or \leq 85
- Night time average \leq 120 and/or \leq 70

HBPM \leq 135 and/or \leq 85

Frequency of assessment: For patients in the standard care arm, blood pressure will be assessed monthly after initiation or change in antihypertensive medication until target blood pressure is reached. Subsequently blood pressure will be monitored every 3 monthly.

Standard care home based BP monitoring: Self-measured BP monitoring be based on 2 measurements taken at least 1 minute apart in the morning and evening (ie, 4 readings per day) optimally for 7 days (ie, 28 readings total) with a minimum of 3 days (ie, 12 readings total). For each monitoring period, the average of all SBP and DBP readings should be obtained to assess BP. If the first day's readings are excluded, the preferred and minimum periods of monitoring should be 8 and 4 days, respectively. (9)

Standard care Office based BP monitoring:y 2–3 office visits at 1–4-week intervals. At each visit take 3 measurements with 1 min between them. Calculate the average of the last 2 measurements. If BP of first reading is <130/85 mmHg no further measurement is required.(10)

Stepwise approach for use of antihypertensive medications

Consider monotherapy in low risk grade 1 hypertension or in very old (> 80 yrs).

Category	Systolic		Diastolic
Normal BP	<130	and	<85
High normal BP	130-139	and/or	85-89
Grade 1 hypertension	140-159	and/or	90-99

Grade 2 hypertension	≥ 160	and/or	≥ 100
----------------------	-------	--------	-------

Table-1 Grades of hypertension

Classification of hypertension risk based on risk factors, end organ damage. (Table-2)

Risk factors/ Hypertension mediated organ damage	High normal blood pressure	Grade 1 hypertension	Grade 2 hypertension

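### Secondary outcome 4 compares raw counts of drug additions and dose increases between arms with different titration rules, so it mixes need for drugs with the tempo of the Group B algorithm

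*Protocol*

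**What the plan says.** **The outcome.** Section 9.2, item 4: "Frequency of introduction of new antihypertensive medications or dose increment of existing antihypertensive medications will be noted across both the groups and compared". Section 4.2, objective 4, matches it: "To study the frequency of introduction of new antihypertensive medications or dose escalation of existing antihypertensive medications in both the groups". Neither names a reference regimen, and neither separates a restart after a planned reduction from escalation above the entry regimen. The design synopsis lists the drug outcome as "Requirement of antihypertensive medications".

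**Group B (section 7.3.2, Table 4, which the list of tables assigns to the intervention arm).** Step-down from Tiers 1 to 4 can follow "1d-BP < 135/85 for 7 consecutive days"; very low readings or symptoms are alternative triggers, and Tier 1 to Tier 0 also requires no end organ damage. Step-up from Tier 1 reads "Move to Tier 2, if (5d-BP > 135/85) && (after staying in this tier for 5 days", and Tiers 0, 2 and 3 use the same condition. The text above the table describes "half dose reduction at weekly intervals with weekly assessment until the lowest dose is reached followed by withdrawal", with a withdrawal period of 2 to 4 weeks.

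**Group A (section 7.3.1).** Drugs are started or raised above 140/90. On timing, "blood pressure will be assessed monthly after initiation or change in antihypertensive medication until target blood pressure is reached", and after that every 3 months. Table 3 has four upward steps. No step-down rule is given for this arm.

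**The concern.** A count of escalations compares two arms fairly only if both have similar occasions to escalate, or if the count is tied to a common reference. Neither holds here. Group B is deliberately taken below its entry regimen and, if pressure rises, brought back up. Each return is recorded as an event although it may only restore what the patient took at entry. Group A has no planned descent, so it has no planned returns to record.

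This does not depend on how a new drug is defined. Tier 2 to Tier 3 is low-dose to full-dose A+C, which is a dose increase of existing drugs on any reading.

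At stake is the answer to objective 4. A real drug-sparing effect could appear as more frequent escalation in Group B, and the synopsis label invites the reader to take that as a greater requirement for drugs.

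**Working it through.** The protocol states no expected value for this outcome, so there is no figure to reproduce. The sample size in section 12.1 rests on systolic pressure and does not enter.

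**1. One patient in each arm.** Both enter on dual full-dose therapy.
- Group B: Tier 3 → 2 (down), 2 → 3 (up), 3 → 2 (down), 2 → 3 (up), 3 → 2 (down). Two dose increases are scored, and the patient ends one tier below entry.
- Group A: stays on the entry regimen. No events are scored.

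The patient on less treatment has the worse score.

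**2. Occasions per year from the stated intervals.**

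| Basis | Interval (days) | 365 / interval |
|---|---|---|
| Group B, shortest Table 4 cycle | 7 + 5 = 12 | 30.4 |
| Group B, 2-week withdrawal, then step-up | 14 + 5 = 19 | 19.2 |
| Group B, 4-week withdrawal, then step-up | 28 + 5 = 33 | 11.1 |
| Group A, monthly review | 30.4 | 12.0 |
| Group A, 3-monthly review | 91.3 | 4.0 |

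Ratios of Group B to Group A:
- 12-day cycle: 30.4/12 = 2.5 and 30.4/4 = 7.6.
- 19-day cycle: 19.2/12 = 1.6 and 19.2/4 = 4.8.
- 33-day cycle: 11.1/12 = 0.9 and 11.1/4 = 2.8.

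These are occasions, not expected events. The 19- and 33-day cycles apply where a step-down withdraws a drug.

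**3. Both rules applied to the same blood pressure process.** A one-year simulation gave both arms identical systolic pressure and no treatment effect. None of the following assumptions comes from the protocol:
- untreated home systolic mean 140, 150 or 160, between-patient SD 10;
- day-to-day SD 5 or 8, with lag-one correlation 0.5;
- 5 or 8 mm Hg per tier, start at Tier 2;
- clinic reading 5 mm Hg above home;
- home readings every day;
- Group A seen at day 30, then 30 days after a step-up and otherwise after 91 days.

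Over the 3 × 2 × 2 = 12 scenarios, mean step-ups per patient were 0.35 to 1.9 in Group A and 7.0 to 19.9 in Group B. With Group B set 10 mm Hg lower (140 against 150), Group B still had about 14 to 17 against 0.9 to 1.6. Group B was higher in every scenario. The sizes belong to the assumptions, and daily readings without a withdrawal period favour fast cycling.

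**The case against.** **Counting rules belong in the SAP.** Whether a restart counts as new can be settled there. But the event, the between-arm comparison and the two titration rules are fixed in the protocol, and the imbalance follows from them. This point stands only in part.

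**Titration is part of Twin Precision Treatment, so the count fairly describes two strategies.** This stands. It justifies keeping the count as a description, but not reading it as requirement for drugs. Objective 4 and item 4 speak only of frequency; requirement is the synopsis wording.

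**The ceiling is not the expected rate.** This stands, for four reasons:
- The 2- to 4-week withdrawal period slows the cycle.
- Section 7.5.2 has home readings on 5 days a week, while Table 4 needs 7 consecutive days. Section 7.4 does not settle this, and the passages must be reconciled.
- The text above Table 4 considers reduction at a target of 130/80 in younger patients, while Table 4 uses 135/85. These must also be reconciled.
- Section 7.5 uses home pressure for titration study-wide, and section 7.5.1 allows extra ambulatory recordings, so Group A may change between scheduled reviews.

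**Outcome 3 already covers net drug use.** Only among patients with adequate control, a subset formed after randomisation. It does not answer objective 4 for everyone.

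**Safety of withdrawal.** A reader might infer that objective 7 is compromised too. The protocol does not support that: item 7 of section 9.2 assesses safety through adverse effects, uncontrolled hypertension and admissions.

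**Conclusion.** The concern holds in a limited form. Followed as written, the between-arm count combines need for drugs with the tempo of the Group B algorithm, and it can run against a true drug-sparing benefit.

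Two stronger readings are tempting and should not be drawn. One is that the count reflects the algorithm alone: a Group B step-up requires a 5-day pressure above 135/85, so need does enter. The other is that escalations will differ 2.5- to 7.6-fold. Those ratios compare a ceiling with scheduled reviews. With the withdrawal period included, the range is 0.9 to 4.8.

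The direction rests on Table 4 and section 7.3.1 being followed as written. The size cannot be fixed from the protocol. The effect is confined to one secondary outcome; the primary comparison of blood pressure is untouched. The change should still be made, because it is cheap and the present comparison can mislead.

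**What to change.** 1. Make the between-arm comparison for outcome 4 the proportion of all randomised patients whose regimen at 6 months, 1 year and 2 years exceeds the end-of-run-in regimen. Exceeding means more drug classes, or a higher dose level of a continued drug. Like-for-like substitutions do not count.
2. Keep the raw count of introductions and dose increases as a description in both arms. Split it into re-escalation after a planned step-down and escalation above the end-of-run-in regimen.
3. Confirm that drugs and doses are recorded at these visits for every randomised patient. Section 9.2, item 3, states 3-monthly drug counts only among patients with adequate control, so complete recording cannot be assumed.
4. Reconcile the 5-day-a-week home readings with the 7-consecutive-day rule, since this determines how often Group B events can occur.

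**Cost.** Items 1 and 2 change endpoint wording and leave treatment alone. Item 3 may need a change to the case report form. Short-lived escalations between visits drop out of the main comparison but remain in the description. Section 10 withdraws patients with uncontrolled pressure, so the new definition also needs a stated rule for patients without a regimen record at a visit.
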